#### 5.6.1. Extent of Exposure

Extent of exposure will be described by a summary of durations in the study and a display of study contrast agent administration modalities.

CONFIDENTIAL	FORM	
STATISTICAL ANALYSIS PLAN N° GDX-44-004		Page 39 / 60
VERSION 1.0      DATED: 09JAN2018		

### 5.6.1.1 Summary of Durations in the Study

The following times will be presented by descriptive statistics:

- Between the inclusion date and the 1st injection of contrast agent (days): date of the 1st injection of contrast agent - date of signature of the ICF.
- Between the 1st and the 2nd injection of contrast agent (days): date of the 2nd injection of contrast agent - date of the 1st injection of contrast agent.
- Between the 2nd injection of contrast agent and the last study visit (days): date of the subject's last study visit - date of the 2nd injection of contrast agent.
- Between the inclusion visit and the last study visit (days): date of the subject's last study visit - date of signature of the ICF.

The table and the listing that will be displayed are detailed in Sections 6.1.3.1 and 6.2.5 respectively.

### 5.6.1.2 Study Contrast Agent Administration Modalities

The following parameters will be presented by descriptive statistics:

- Location of injection site: Antecubital vein; Other (to be specified).
- Theoretical volume as per IWRS (mL).
- Volume of study contrast agent actually administered (mL).
- Occurrence of an overdose: Yes; No.
- Actual injection rate (mL/s): as a quantitative variable and as a categorical variable in 3 categories (< 2 mL/s, [2 ; 3] mL/s and > 3 mL/s).
- Mode of injection: Manual; Power injector.

The following parameters will be listed only:

- Number of vials dispensed: 1; 2; 3.
- Reason why the volume actually administered is different from the theoretical calculated volume as per IWRS (free specification).

The table and the listing that will be displayed are detailed in Sections 6.1.3.1 and 6.2.5 respectively.

### 5.6.2. Adverse Events

AEs will be coded using MedDRA dictionary version 20.1. The time period for the assessment of AEs is the time interval between the signature of the ICF and the subject's study end. AEs will be described systematically in terms of number and percentage of subjects with AEs and in terms of number of AEs. AEs will be displayed by period (MRI 1 and MRI 2) and overall.

TEAEs will be defined as follows:

- If the AE starts prior to the 1st injection then the AE is not emergent (pre-injection).
- If the AE starts after the 1st injection, then the AE is emergent (post-injection).
  - If it starts between the 1st injection and the 2nd injection (<), then it will be considered as an emergent AE associated with the 1st contrast agent of the subject's sequence.
  - If it starts after the 2nd injection ( $\geq$ ), then it will be considered as an emergent AE associated with the 2nd contrast agent of the subject's sequence.

CONFIDENTIAL	FORM	
STATISTICAL ANALYSIS PLAN N° GDX-44-004		Page 40 / 60
VERSION 1.0      DATED: 09JAN2018		

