### **Study duration**

Minimum study duration for subjects: 4 days

Maximum study duration for subjects: 22 days

The study includes a maximum of 5 visits:

- One screening visit up to 7 days prior to inclusion (screening could be done the same day as the inclusion visit if all the inclusion/exclusion criteria are met)
- Two sequential imaging visits (minimum interval 2 days and up to 14 days): each visit will consist of a P03277 injection or MultiHance® injection and MRI procedure (if during the first visit the MRI procedure is performed with P03277 injection then the second visit will be done with MultiHance® injection and vice versa for the other series) .
- Two safety visits: 1 day after each injection and MRI examination.

The study will be considered as completed once all the images collected for all the subjects will have been reviewed by all the independent blinded readers.

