In addition of these subjects, two hundred and forty (240) subjects will be enrolled in a second subset (subset 2, see [Figure 1](#)). These subjects will be used for dose-finding part of the study in which the safety and diagnostic efficacy of P03277 will be evaluated in CNS MRI at doses of 0.025, 0.05, 0.1 and 0.2 mmol/kg (doses driven by efficacy in a safety acceptable range) with a 1:1:1:1: ratio versus MultiHance® (0.1 mmol/kg BW).

Subjects from both subsets will receive one of the doses of P03277 and one dose of MultiHance® by single IV injection at a rate of 2 mL/second followed by 0.9% saline flush in randomized order in two successive treatment periods separated by a wash out period of 2 days minimum up to 14 days.

During the course of the study, 2 MRIs will be obtained from each subject: one unenhanced and P03277-enhanced MRI; and one unenhanced and MultiHance®-enhanced MRI. MRI evaluations will be performed by on-site investigators and 3 independent off-site blinded readers.

To determine the exact matching of lesions throughout the different imaging sequences and MRI examination (P03277 and MultiHance®), an independent radiologist (lesion tracker) will perform 'lesion tracking' (except for the global matched pairs evaluation) based on the available CNS (brain/spinal cord) diagrams 

 CONFIDENTIAL	Protocol No. GDX-44-004 Version No. 2.0 (Protocol including amendment n°1) Date: 11 July , 2016	 Page 24 / 84
----------------------------------------------------------------------------------------------------------	----------------------------------------------------------------------------------------------------------	-----------------------------------------------------------------------------------------------------

The safety of subjects will be assessed using vital signs, 12-lead ECGs, injection site tolerance, clinical laboratory parameters (blood and urine) and by monitoring of adverse events (AEs). Safety assessments will be conducted over 1 day follow-up period after each MRI visit.

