**Table 5: Time period for the assessment of AEs**

		Start	End
Period 1	Before treatment	Informed consent signature	Start of study treatment of the first MRI
Period 2	Period of first MRI	Start of study treatment of the first MRI	Start of study treatment of the second MRI
Period 3	Period of second MRI	Start of study treatment of the second MRI	End of study

Events will be classified by period according to time of onset.

 CONFIDENTIAL	Protocol No. GDX-44-004 Version No. 2.0 (Protocol including amendment n°1) Date: 11 July , 2016	 Page 65 / 84
---------------------------------------------------------------------------------------------------	----------------------------------------------------------------------------------------------------------	-----------------------------------------------------------------------------------------------------

Events will be classified as treatment-emergent if they started or increased in severity during period 2 or period 3. This will also include events with missing intensity if the end time is after induction or missing.

Partial start dates/times will be queried. If information is not available to reliably allocate to a session and period, the allocation will be agreed at the data review meeting before database lock. If there is any doubt about treatment emergence, AEs will be classified as treatment emergent.

In all summaries, recurring AEs (AEs classified with the same preferred term) for a given subject in a given period will be counted as a single AE. If severity is summarized, this will be the maximum severity.

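### Adverse events count against the first agent for 2 to 14 days but against the second for about 1 day, so the planned MRI 1 and MRI 2 columns are not comparable

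*SAP*

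**What the plan says.** Protocol 3.1 describes symmetric follow-up: "Safety assessments will be conducted over 1 day follow-up period after each MRI visit". The two injections are given "in two successive treatment periods separated by a wash out period of 2 days minimum up to 14 days".

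The attribution of adverse events is not symmetric. In protocol Table 5, Period 2 runs from the first study treatment to the second, and Period 3 from the second to the end of the study. "Events will be classified by period according to time of onset". SAP 5.6.2 follows the same boundaries. Its overall span is stated thus: "The time period for the assessment of AEs is the time interval between the signature of the ICF and the subject's study end". If an event starts between the injections, "then it will be considered as an emergent AE associated with the 1 st contrast agent of the subject's sequence". If it starts at or after the second injection, "then it will be considered as an emergent AE associated with the 2 nd contrast agent of the subject's sequence".

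Note 8 to the protocol flow chart ends collection at the last evaluation, 1 day after the last injection. The exception is a related event of which the investigator later becomes aware. Protocol 9.1.4 has adverse events assessed at visit 4 before the second injection, so events that start after visit 3 do enter the first agent's count.

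SAP 5.6.2 reports numbers and percentages of subjects and numbers of events, and states that "AEs will be displayed by period (MRI 1 and MRI 2) and overall". SAP 5.6.2.1 to 5.6.2.4 present treatment-emergent adverse events (TEAEs) by dose and period. Under SAP 5.6, an agent group takes in everyone who received that agent, in either period. The available text sets no common window, no cut on time of onset and no rate per person-day. SAP 5.6.1.1 describes the intervals but does not link them to event rates. The SAP section 6 table list and the shells could not be read, so this statement covers the text only.

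**The concern.** Two columns that look parallel rest on follow-up of very different length. With any background rate of events in this population, MRI 1 will show more than MRI 2, and a reader may take that for a first-exposure or period effect. In the columns that pool both periods, an agent's incidence mixes a long window in about half of its exposures with a short one in the rest. It then estimates neither a 1-day nor a longer risk, and later events are under-ascertained. This matters because the primary objective asks for a dose that is safe as well as effective, and SAP 5.5.1.5 selects the dose on benefit and risk.

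**Working it through.** **Inputs.** From the documents: screening up to 7 days before the first MRI; 2 to 14 days between injections; collection to 1 day after the second injection; 1:1 sequence (SAP 1.2); 50 + 10 = 60 subjects per dose in subset 2 (protocol 8). Event rates, delayed-event risks and sequence imbalances below are assumptions; the documents give none.

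**1. The plan's own figure.** Protocol 3.2 gives 4 to 22 days per subject. Maximum: 7 + 14 + 1 = 22. Minimum: 0 + 2 + 1 = 3 elapsed days, or 4 calendar days. Both reproduce with a 1-day window after the second injection.

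**2. Window ratio.** First agent 2 to 14 days, second agent 1 day: 2:1 to 14:1. SAP 5.2.2 treats a gap of more than 14 and up to 21 days as a non-major deviation, so 21:1 can occur without exclusion from the per-protocol set. First-period exposures supply T/(T+1) of an agent's at-risk days: 67% at T = 2, 88% at T = 7, 93% at T = 14.

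**3. Background alone, no drug effect.** With a constant rate λ per day, the share of subjects with an event is 1 − exp(−λT).

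| Column | λ = 0.005 | 0.01 | 0.02 | 0.05 | Ratio to MRI 2 |
|---|---|---|---|---|---|
| MRI 2, 1 day | 0.5% | 1.0% | 2.0% | 4.9% | 1 |
| MRI 1, 2 days | 1.0% | 2.0% | 3.9% | 9.5% | about 2.0 |
| MRI 1, 7 days | 3.4% | 6.8% | 13.1% | 29.5% | 6.9 to 6.1 |
| MRI 1, 14 days | 6.8% | 13.1% | 24.4% | 50.3% | 13.6 to 10.3 |

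For numbers of events, the expected ratio is simply the window ratio. With a common 1-day window, both columns would show the MRI 2 row.

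**4. Events starting after day 1 and before the second injection.** Of 60 subjects on a dose, about 30 receive it first and are followed beyond day 1. For a true risk r per exposure, the displayed incidence is about r/2 if nothing is reported outside scheduled follow-up: 1.0% for r = 2%, 2.5% for r = 5%. The chance of at least one case, 1 − (1 − r)^n, falls from 70.2% (n = 60) to 45.5% (n = 30) for r = 2%, and from 95.4% to 78.5% for r = 5%.

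**5. Agent contrast.** At 0.02 per day and 14 days, an exact 1:1 split gives (24.4 + 2.0)/2 = 13.2% for both agents, so there is no bias. If 60% of a dose group received P03277 first, P03277 would show 0.6 × 24.4 + 0.4 × 2.0 = 15.4%, and MultiHance in the same subjects 0.4 × 24.4 + 0.6 × 2.0 = 11.0%.

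**6. Dilution.** At 1% per day and 7 days, the pooled background is (6.8 + 1.0)/2 = 3.9%. A true 3-point excess on day 1 appears as 6.9% against 3.9%, where a common 1-day window gives 4.0% against 1.0%. The difference is 3.0 points under both rules; the ratio is 1.8 rather than 4.0. The background variance p(1 − p) rises from 0.010 × 0.990 = 0.0099 to 0.039 × 0.961 = 0.0375, about 3.8 times.

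**The case against.** The strongest reply is that the comparison that matters is protected. Sequence is randomised 1:1. Within the MRI 1 column both agents share the long window, and within MRI 2 both share the short one, so the by-period display keeps agents and doses like for like inside each column. The safety tables are descriptive: no test, no ratio and no MRI 1 versus MRI 2 comparison is planned. SAP 5.6.2.3 has separate tables for events related to the product, the listings give onset times, and SAP 5.6.1.1 will show the unequal intervals. Scheduled vital signs, ECG, laboratory and injection-site checks cover 1 day after both injections.

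Most of this stands, and it rules out three stronger readings that a reader might infer.

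- *That the P03277 versus MultiHance difference is biased.* It is not, in expectation. The dilution in step 6 affects the ratio and the noise, not the risk difference.
- *That a late reaction can be counted only when the agent came first.* Flow-chart note 8 and protocol 10.2.1 and 10.2.2 provide for reporting of related events after the last visit, so the halving in step 4 applies to systematic, all-cause collection. Whether such late reports enter the tables is unclear, since the SAP's assessment period stops at study end.
- *That subjects withdrawn before visit 4 distort the second agent's percentages.* Under SAP 5.6 they never enter its denominator.

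The reply does not rescue the period columns. Setting them side by side invites a comparison that they cannot support. The columns that pool both periods still mix windows, and unscheduled reporting does not replace follow-up.

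**Conclusion.** The point holds for the period columns and for the absolute incidence of later events. The windows differ by 2:1 to 14:1 as scheduled, which follows from the documents without any assumption. The resulting excess at MRI 1, about 2 to 14 times, assumes a constant background rate of 0.5% to 5% per day. All-cause events after day 1 are systematically collected for about half of each agent's exposures. The documents do not support a claim of bias between agents: that contrast is unbiased in expectation, with added background noise and sensitivity to a chance sequence imbalance within a dose. The correction is worth making before the tables are produced, because it is cheap and the columns as planned can mislead.

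**What to change.** In SAP 5.6.2, keep the Table 5 classification and all the planned TEAE tables. Add TEAE summary tables and tables by system organ class and preferred term, by agent, dose and period, restricted to one common window: onset from injection to the 1-day safety visit (visit 3 or visit 5). State that these tables serve any comparison between periods and are the like-for-like display of agents and doses. Show events that start after visit 3 and before the second injection in a separate table, labelled as systematically collected for the first agent only. Record the addition in SAP section 4.

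The cost is one variable derived from onset times already collected, and the extra tables; no visit is added. The common-window tables leave out later events. They should therefore stand beside the all-TEAE tables and not replace them: replacement would remove late events from the main display and depart from Table 5, whose periods are meant to cover all events.

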### 3.5.3. Missing and Partially Known AE Start Dates

If an AE start date is missing or unknown, the AE will be considered as treatment emergent.

When the start date of an AE is only partially known, it will be categorized as not emergent or emergent using the following rules:

- If the partial start date is before ( $<$ ) the injection at the 1st MRI procedure visit date (i.e., year or year & month is/are before those of the date of the injection) then the AE is not emergent.
- If the partial start date is after ( $\geq$ ) the injection at the 1st MRI procedure visit date (i.e., year or year & month is/are the same as or after those of the date injection) then the AE is emergent.

CONFIDENTIAL	FORM	
STATISTICAL ANALYSIS PLAN N° GDX-44-004		Page 16 / 60
VERSION 1.0      DATED: 09JAN2018		

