#### 4. CHANGES IN THE CONDUCT OF THE STUDY OR PLANNED ANALYSES

The protocol was amended on one occurrence. See amended protocol for a full list of changes.

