#### RATIONALE FOR ANY DEVIATION FROM PRE-SPECIFIED ANALYSIS PLAN PERFORMED

It was planned in the protocol to repeat on the PPS the evaluation of secondary efficacy criteria in case of a difference from the FAS by more than 15%. It has been decided that only the analyses of data from off-site readings for some relevant secondary criteria will be repeated on the PPS.

Further, three secondary criteria have been added since the last amendment: The Contrast-to-Noise Ratio calculated based on the noise issued from the CerebroSpinal Fluid (CSF): CNRCSF, the Lesion-to-Brain Ratio (LBR) and the Contrast enhancement percentage. The three criteria are calculated by subject, and by independent blinded reader in a centralized procedure (off-site readers) and the result is provided by exam for each reader by averaging the parameter for maximum 3 enhanced lesions.

$\text{CNR}_{\text{CSF}}$  is derived for each lesion, from the SI measurement, according to the following formula:

$$\text{CNR}_{\text{csf}} = \frac{SI_{\text{lesion}} - SI_{\text{ht}}}{SD_{\text{noise}}}$$

where  $SJ_{lesion}$  = the SJ in the ROJ in the lesion.

$SI_{bt}$  = the SI in the ROI in the lesion.

SDnoise ≡ SD of CSF noise

LBR is derived for each lesion, from the SI measurement, according to the following formula:

$$\text{LBR} = \frac{SIlesion}{SIht}$$

where  $SJ_{lesion}$  = the SJ in the ROI in the lesion.

$SI_{ht}$  = the SI in the ROI in the lesion.

Contrast enhancement percentage is derived for each lesion, from the SI measurement, according to the following formula:

$$\text{Contrast Enhancement Percentage} = \frac{SI_{post} - SI_{pre}}{SI_{pre}}$$

where  $SI_{post}$  = the SI in the ROI in the lesion post contrast media administration.  
 $SI_{pre}$  = the SI in the ROI in the lesion pre contrast media administration.

These three criteria will be analyzed as the primary criterion.

CONFIDENTIAL	FORM	
STATISTICAL ANALYSIS PLAN N° GDX-44-004		Page 18 / 60
VERSION 1.0      DATED: 09JAN2018		

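### SAP 5.6.2 drops worsening from the protocol's definition of a treatment-emergent AE without declaring it; separately, a same-period baseline would be a cheap addition for the agent given second

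*SAP*

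**What the plan says.** **Treatment emergence.** Protocol 12.4, below Table 5, has two limbs: "Events will be classified as treatment-emergent if they started or increased in severity during period 2 or period 3". Periods 2 and 3 together run from the first injection to the end of study. For incomplete records it adds "This will also include events with missing intensity if the end time is after induction or missing", and for unclear cases "If there is any doubt about treatment emergence, AEs will be classified as treatment emergent". Allocation to a period is by start: "Events will be classified by period according to time of onset".

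SAP 5.6.2 keeps only the onset limb. If an AE begins before the first injection, the rule is "injection then the AE is not emergent (pre-injection". An AE that begins between the injections goes to the first agent, and a later one to the second. SAP 3.5.3 does the same for partial start dates: "it will be categorized as not emergent or emergent using the following rules". Those rules compare only the start date with the date of the first injection.

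SAP Section 4 records departures from the protocol. On the amendment it says "See amended protocol for a full list of changes". It then declares two analysis changes. One narrows the per-protocol repeat ("It was planned in the protocol to repeat on the PPS the evaluation of secondary efficacy criteria"); the other adds three efficacy criteria. It says nothing on AEs.

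**Baseline for change.** SAP 5.6.4, 5.6.5.1 and 5.6.5.2 measure laboratory, ECG and vital-sign change after either agent from the value taken before the first injection. Note 10 to the protocol's flow chart (Table 1) and the ECG text of 7.2.8 also use visit 2. For vital signs, however, protocol 7.2.8 labels the value before each injection as baseline. SAP 3.1 does not say which injection it means. SAP 5.6 groups safety data by the agent received in either period, and SAP 5.4 says that period appears only in the AE tables.

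**The concern.** A safe dose is part of the primary objective, and the safety profile of P03277 against MultiHance is a secondary one. The by-agent treatment-emergent tables are the main display of that comparison. The SAP states that it rests on protocol Version 2.0, the version that holds the severity limb. A reader who knows the protocol would therefore assume that worsening is counted, and nothing in the SAP says otherwise.

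For the change tables, the agent given second inherits whatever happened between the two visits. A subject may be counted under that agent for a QTc rise above 60 ms, or put in a laboratory shift class, because of a shift already present before the agent was injected. A subject may also be missed for the same reason.

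**Working it through.** **Part 1: the two definitions side by side (known start date)**

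| AE | Protocol 12.4 | SAP 5.6.2 |
|---|---|---|
| Starts after first injection | emergent | emergent |
| Starts before, never worsens | not emergent | not emergent |
| Starts before, worsens after, one AE record | emergent | not emergent |
| Starts before, worsens after, worsening entered as a new AE | emergent | emergent, through the new record's onset |

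1. Only the third row differs, and in one direction. On this point the SAP count is equal to or lower than the protocol count.
2. Whether the third row arises depends on site recording. Protocol 10.1.2 requires AEs to be collected before any injection. Protocol 10.1.3 lists one onset and one intensity per AE and gives no rule for recording a change in intensity.
3. An AE in the third row appears only in the Extended Set summary, which has a single total column (SAP 5.6.2.1), and in the listings.
4. The amendment does not explain the difference. The amended protocol, to which Section 4 points, is the document that contains the limb.
5. Restoring the limb alone leaves a gap. The protocol allocates periods by onset, so a worsening of an AE that began before the first injection has no agent assigned to it.
6. The missing-intensity rule is also absent from the SAP, and neither document defines the induction it refers to.

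The documents give no rate of pre-injection AEs or of worsening, so no count can be computed.

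**Part 2: what the second agent's change contains**

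Let pre1 and pre2 be the values before the first and second injections, and post2 a value after the second.

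- Difference: post2 − pre1 = (post2 − pre2) + (pre2 − pre1).
- Relative change: post2/pre1 = (post2/pre2) × (pre2/pre1).

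ECG has 4 time points per injection, so 4 × 2 − 1 = 7 after baseline. Of these, 3 follow the second injection and carry the pre2 − pre1 term; 1, just before that injection, is the term itself. For laboratory change, visit 5 carries it and visit 4 is it.

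Illustrative values, not from the documents:

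| pre1, pre2, post2 | SAP change | Same-period change |
|---|---|---|
| QTc 400, 430, 465 ms | 65 (counted as >60) | 35 (not counted) |
| QTc 400, 375, 440 ms | 40 (not counted) | 65 (counted) |
| Creatinine 60, 69, 76 µmol/L | 76/60 − 1 = +26.7% | 76/69 − 1 = +10.1% |

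In each example pre2 lies inside the QTc or creatinine limits in protocol 11.2 (+30 ms; −25 ms; +9 µmol/L, or 15%), so those limits would not have prevented the second injection.

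The term reaches the mean changes, the count of QTc rises above 60 ms, and the shift tables for creatinine, eGFR, BUN and cystatin C. It does not reach QTc above 450 or 500 ms, or the vital-sign and laboratory out-of-range counts.

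Effect on the comparison of agents: SAP 1.2 randomises order 1:1. If the mean drift d is the same in both orders and both periods are pooled, each agent's mean change gains d/2 and the difference between agents is unchanged. Spread does increase. Assume between-visit variance is r times within-visit variance; the documents give no r. The variance of change for second exposures is then multiplied by 1 + r: 1.5, 2 and 3 for r = 0.5, 1 and 2.

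**The case against.** **On part 1.** A reader might infer that the by-agent tables certainly leave out a class of events. The documents do not support that. Protocol 10.1.3 treats an AE in the pre-administration period as not related, so a worsening judged related fits poorly on the old record and may well be entered anew. Clinically significant vital-sign, ECG and laboratory changes are AEs in their own right (protocol 7.2.8 and 9.5.1), and SAEs are listed by contrast agent group (SAP 5.6.3). This is inference about site practice and settles nothing, but it makes the loss conditional.

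A reader might also take a size from the screening window, 7 of 7 + 14 + 1 = 22 days (32%), or from the weight of one subject in a planned dose group, 1/60 = 1.7 percentage points. The first is a share of time and the second the reciprocal of a column size. Neither measures how many AEs are affected. Screening may also fall on the day of visit 2, which leaves almost no window.

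Protocol Section 12 describes itself as a summary that the SAP completes. That allows added detail; it does not account for the silent removal of a limb.

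**On part 2.** A reader might infer that the single baseline is an error, or that it biases P03277 against MultiHance. Neither holds. For ECG and laboratory data the SAP follows the protocol, and with balanced order a common drift is noise between agents. Nor can the SAP be faulted for an unclear table layout: Section 6 is not readable in the available copy and the shells are separate attachments. Same-period tables may already be planned there. In addition, the visit 4 laboratory row and the ECG row before the second injection may already show the mean shift. Subtracting rows could then recover a mean same-period change if the rows hold the same subjects, but not its spread, the count above 60 ms or the shift classes.

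**Conclusion.** Part 1 stands as an undeclared difference between protocol and SAP, and should be corrected. Its effect depends on the site not entering the worsening as a new AE. The number of AEs cannot be derived and is probably small, and the direction is fixed: too few treatment-emergent AEs, never too many.

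Part 2 stands as an inexpensive improvement. It is not a departure for ECG or laboratory data. It matters for individual classification, not for the average difference between agents, provided that drift does not depend on which agent came first. The size of the drift is not in the documents, and the final table layout cannot be confirmed. The one real contradiction is the vital-sign baseline: note 10 to Table 1 and SAP 5.6.5.2 use the first injection, while the vital-sign text of protocol 7.2.8 uses each injection.

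The primary CNR analysis, its alpha and the sample size are untouched.

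**What to change.** **Part 1**
- In SAP 5.6.2, restore the limb: an AE that starts before the first injection and becomes more severe after it is treatment-emergent. Attribute the worsening to the agent most recently injected before it. AEs that start after the first injection stay assigned by onset, as in both documents. Alternatively, declare and justify the removal in Section 4.
- State whether sites enter a worsening as a new AE.
- Clarify the reference to induction before carrying over the missing-intensity rule.
- Leave the protocol's rule for doubtful cases as it is.

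Cost: SAP wording. Because the date of a worsening may not be recorded, some AEs may need a query before database lock.

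**Part 2**
- Keep the visit 2 baseline tables. The protocol sets that baseline for ECG and laboratory data, and they show cumulative change.
- Add change by agent from the same-period pre-injection value (visit 2 for the first agent, visit 4 for the second). Cover vital signs, QTc with the count above 60 ms, and creatinine, eGFR, BUN and cystatin C with their shift tables.
- Reconcile the vital-sign baseline across Table 1 note 10, protocol 7.2.8 and SAP 5.6.5.2, and say in SAP 3.1 which injection is meant.

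Cost: a few extra descriptive tables. No new data are needed, since protocol 9.1.4 already collects vital signs, triplicate ECG and blood before the second injection.
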